13.5 Interim Analysis

No Interim Analysis will be performed for this study.

14.0 Adverse Events and Classifications

AE and AE subcategories are defined per ISO14155:2011, as described below.

14.1 Adverse Event (AE)

An AE is any untoward medical occurrence, unintended disease or injury, or untoward clinical signs (including abnormal laboratory findings) in subjects, whether or not related to the investigational medical device.

This definition includes events related to the investigational medical device or the comparator and the procedures involved.

AEs will be collected starting from the time subject is enrolled until the follow-up period is completed.

14.2 Serious Adverse Event (SAE)

A Serious AE (SAE) is an AE that has

- a) Led to death,
- b) Led to serious deterioration in the health of the subject, that either resulted in
 - 1) A life-threatening illness or injury, or
 - 2) A permanent impairment of a body structure or a body function, or
 - 3) In-patient or prolonged hospitalization, or

Document Title: Randomized Controlled Study Comparing Colon Evaluation With The Pure-Vu System To A Standard Colonoscopy In Patients Who Are High Risk For Inadequate Bowel Preparation ("RESCue")	Document No. CL00048	Version 1.0	Page 28 of 41
---	--------------------------------	-----------------------	---------------

4) Medical or surgical intervention to prevent life-threatening illness or injury or permanent impairment to a body structure or a body function,

c) Led to fetal distress, fetal death or a congenital abnormality or birth defect

NOTE: Planned hospitalization for a pre-existing condition, or a procedure required by the clinical investigational plan, without serious deterioration in health, is not considered an SAE.

Some important medical events, although they may not result in death, be life-threatening, or require hospitalization may still be considered SAEs when, based upon appropriate medical judgment, they are felt to jeopardize the subject and may require medical or surgical intervention to prevent one of the outcomes listed above.

Life threatening means that the subject was, in the view of the investigator, at immediate risk of death from the reaction as it occurred. This does not include an AE that, if more severe, might have caused death.

Disability means a substantial disruption of a person's ability to conduct normal life's functions.

14.3 Adverse Device Effect (ADE)

An Adverse Device Effect (ADE) is an AE related to the use of an investigational medical device.

This definition includes AEs resulting from insufficient or inadequate instructions for use, deployment, implantation, installation, or operation, or any malfunction of the investigational medical device.

This definition includes any event resulting from use error or from intentional misuse of the investigational medical device.

14.4 Serious Adverse Device Effect (SADE)

A Serious Adverse Device Effect is an adverse device effect that has resulted in any of the consequences characteristic of an SAE.

14.5 Unanticipated Serious Adverse Device Effect (USADE)

An Unanticipated Serious Adverse Device Effect is a serious adverse device effect which by its nature, incidence, severity, or outcome has not been identified in the current version of the risk analysis report.

Document Title: Randomized Controlled Study Comparing Colon Evaluation With The Pure-Vu System To A Standard Colonoscopy In Patients Who Are High Risk For Inadequate Bowel Preparation (“RESCue”)	Document No. CL00048	Version 1.0	Page 29 of 41
---	--------------------------------	-----------------------	---------------

14.6 Classification of Event Severity, Relationship and Outcomes

Adverse Event Severity Classification

Severity will be defined according to the following criteria:

- **Mild:** Awareness of event, but easily tolerated
- **Moderate:** Discomfort enough to cause some interference with activities of daily living (ADL)
- **Severe:** Incapacitating, with an inability to perform ADL

An AE can be classified as severe and not deemed a SAE. Similarly, a SAE is not automatically severe in nature.

Adverse Event Relationship Classification

Relationship to study device administration will be determined as follows:

- **No Relationship:** No relationship between the AE and the administration of study device and a known relationship to other etiologies such as concomitant medications, procedure, or subject's clinical state.
- **Possible Relationship:** An AE that follows a reasonable temporal sequence from administration of the study device and follows a known response pattern to the study device but could have been produced by the participant's clinical state or by other therapies.
- **Probable Relationship:** An AE that follows a reasonable temporal sequence from administration of the study device; follows a known response pattern to the study device; and cannot be reasonably explained by the known characteristics of the participant's clinical state or by other therapies.
- **Definite Relationship:** An AE that follows a plausible temporal sequence from administration of the study device and follows a known response pattern to the study device. The reaction cannot be reasonably explained by the known characteristics of the subject's clinical state or other therapies administered to the subject.
- **Unknown/Impossible to Determine:** Given the information available, sequence and timing of events, it is unknown or impossible to determine the relationship of the AE with the study device.

Document Title: Randomized Controlled Study Comparing Colon Evaluation With The Pure-Vu System To A Standard Colonoscopy In Patients Who Are High Risk For Inadequate Bowel Preparation (“RESCue”)	Document No. CL00048	Version 1.0	Page 30 of 41
---	--------------------------------	-----------------------	---------------

Adverse Event Outcome Classification

Outcome of the event will be defined according to the following:

- ***Resolved:*** The event has fully resolved at the end of the study.
- ***Resolved with sequelae:*** The event has resolved, but retained pathological conditions resulting from the prior disease or injury.
- ***Ongoing:*** The event is ongoing at the end of the study.
- ***Death:*** This event is determined to be the cause of death.

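### Section 14.6 makes a known response pattern a condition of every related rating, so a device harm new in kind can only be rated Unknown

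*Combined protocol and SAP*

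**What the plan says.** Section 14.6 presents five categories as the method for settling whether an event is related to the device. Three of them express a relationship:

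- Possible: "An AE that follows a reasonable temporal sequence from administration of the study device and follows a known response pattern to the study device", where the subject's condition or other therapies could also have produced it.
- Probable: reasonable timing, and an event that "follows a known response pattern to the study device; and cannot be reasonably explained" by those other causes.
- Definite: "An AE that follows a plausible temporal sequence from administration of the study device and follows a known response pattern to the study device", again with no other reasonable explanation.

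The other two are No Relationship, defined as "No relationship between the AE and the administration of study device and a known relationship to other etiologies", and Unknown/Impossible to Determine, for cases where "it is unknown or impossible to determine the relationship of the AE with the study device".

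The device-effect definitions form a chain. Section 14.3: "An Adverse Device Effect (ADE) is an AE related to the use of an investigational medical device". Section 14.4: "A Serious Adverse Device Effect is an adverse device effect that has resulted in any of the consequences characteristic of an SAE". Section 14.5 defines a USADE as a SADE "which by its nature, incidence, severity, or outcome has not been identified in the current version of the risk analysis report". Section 14.3 also counts events from inadequate instructions, malfunction, use error and intentional misuse as ADEs.

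Two duties turn on relatedness. Under section 14.8, AEs are followed until the subject completes the study, but those the investigator considers device-related are followed to resolution where possible. Under section 14.9, the investigator reports ADEs, SADEs and USADEs, as well as all SAEs, to the sponsor and the IRB.

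**The concern.** A relatedness scale should be able to register an effect that nobody has seen before. In section 14.6 prior knowledge of the effect is a necessary condition, joined to timing, in every category that expresses a relationship. Section 14.5, by contrast, expressly allows for a device effect that is unanticipated in its nature, and such an effect must first be related to the device.

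At stake is how a new kind of harm in the Pure-Vu arm would be labelled, reported and followed. Investigators at up to four sites (section 3.0) could also rate the same event differently, depending on how literally they apply the condition.

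**Working it through.** No arithmetic applies beyond counting; the check sets the definitions side by side.

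**Step 1. Test case.** Take a harm that arises in normal use, with reasonable timing, no known response pattern and no known other etiology, and with no malfunction, use error, misuse or instruction failure behind it. In case (a) another cause is conceivable. In case (b) no other cause reasonably explains it.

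| 14.6 category | Condition that decides | Case (a) | Case (b) |
|---|---|---|---|
| No Relationship | a known other etiology | fails | fails |
| Possible | known pattern | fails | fails |
| Probable | known pattern | fails | fails |
| Definite | known pattern | fails | fails |
| Unknown | relationship cannot be determined | fits | only category left, though the wording fits poorly |

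The pattern condition stands in 3 of 5 categories, which are all 3 of the related ones. Related ratings open to this harm: 0 of 3.

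**Step 2. The chain.** USADE requires SADE (14.5), SADE requires ADE (14.4), and ADE requires relatedness (14.3). If related means a 14.6 rating of Possible, Probable or Definite, the harm in step 1 cannot be an ADE, and so cannot be a SADE or USADE. If Unknown counts as related, or if relatedness in 14.3 and 14.8 is settled independently of 14.6, this does not follow. The protocol does not say which applies.

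**Step 3. How much of 14.5 is touched.** Section 14.5 has four limbs: nature, incidence, severity and outcome. An event of a known kind can pass the pattern test and still be unanticipated on the last three. Only 1 of 4, nature, is touched, and only in part. A known response pattern, which 14.6 leaves undefined, is a different test from being identified in the risk analysis report. A pattern known from elsewhere but absent from that report would meet 14.6 and still be unanticipated under 14.5.

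**Step 4. Consequences, if the link in step 2 exists.**
- Non-serious new harm: it may miss the ADE report in 14.9 and follow-up to resolution in 14.8. AE collection then ends with the follow-up period (14.1), that is, the call 1-3 business days after the procedure (12.5).
- Serious new harm: it is still reported under 14.9 as an SAE (24 hours, at the latest 10 working days), but without the SADE or USADE label.

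**Step 5. What is not affected.** Events from malfunction, use error, misuse or inadequate instructions are ADEs under 14.3 with no pattern test. Section 14.8 has every AE recorded whatever its relationship. Sponsor or CRO staff have access to the database (16.1), and CRFs are reviewed regularly (16.0). The AE comparison in 13.4 applies no relatedness filter. The primary endpoint (9.1) is a cleansing score.

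**Step 6. Size.** The documents give no rate for harms new in kind, so no frequency is claimed. By design, only the Pure-Vu arm, 44 of 88 planned subjects, is exposed to the device.

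**The case against.** The strongest reply is that the conflict depends on a link the protocol never makes. Section 14.3 defines an ADE without citing 14.6, and 14.8 turns on the investigator's determination, also without citing it. Section 14.3 even admits whole classes of event with no pattern test, which suggests that ADE status is not governed by the 14.6 scale alone. This stands, and it makes the consequences conditional. It does not remove the defect inside 14.6, which prescribes its criteria and offers no override.

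The safeguards in step 5 also stand and keep the impact small.

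A further objection concerns cost. Without the pattern condition, Possible rests on little more than timing. Section 5.1 reports minor symptoms in up to one third of colonoscopy patients; 44 × 1/3 = 14.7, so up to about 15 in the Pure-Vu arm. That is not a count of extra ADEs. Section 7.1 expects complications similar to those of colonoscopy and names pain among them, so such symptoms would largely pass the pattern test already. The objection is right that some increase must be expected and stated.

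A reader might infer three stronger claims that the documents do not support:
- That the nature limb of 14.5 can never be met. Step 3 shows that it is narrowed, not emptied.
- That a serious new harm would go unreported. Section 14.9 requires reporting of SAEs whatever their relationship.
- That the sponsor's report to FDA would fail. Section 14.9 attaches that report to the sponsor's own evaluation of an unanticipated effect and does not make it depend on the investigator's 14.6 rating.

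**Conclusion.** The point holds, and its severity is minor. That section 14.6 excludes a harm new in kind from every related rating follows directly from its wording. That this changes reporting or follow-up rests on one assumption, that the 14.6 rating decides relatedness for 14.3-14.5, 14.8 and 14.9. On that assumption the exposure is limited to the ADE report and follow-up to resolution for a non-serious new harm, and to the SADE or USADE label for a serious one. The conclusion covers only harms arising in normal use that match no pattern known from any source.

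**What to change.** In section 14.6, make a known response pattern supportive evidence and not a requirement for at least Possible and Probable, keeping reasonable timing and the existing wording on alternative causes. Case (a) above would then be rated Possible and case (b) Probable. Keeping the condition in Definite would preserve a difference from Probable, since the two are otherwise worded almost alike.

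In the same edit, state which ratings count as related for 14.3-14.5, 14.8 and 14.9, and that the sponsor reviews each event rated Unknown for possible ADE, SADE or USADE status.

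The cost is a wording change in the protocol and the AE form guidance, plus the sponsor's review of Unknown events. Some additional time-related events in the Pure-Vu arm would be rated Possible and, if Possible counts as related, reported as ADEs under 14.9. Their number cannot be estimated from the documents. Design and sample size do not change.

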14.7 Device Deficiencies

A device deficiency is an inadequacy of a medical device related to its identity, quality, durability, reliability, safety, or performance, such as malfunction, misuse or use error and inadequate labeling.

All device deficiencies will be documented and the device should be returned to Motus GI for analysis, if possible. Instructions for returning the investigational device will be provided. Device deficiencies should also be documented in the subject’s medical record.

Device deficiencies are NOT AEs. However, if there is an AE that results from a device deficiency, that specific event would be recorded on the appropriate CRF.

14.8 Adverse Event Recording and Reporting

Assessment of the occurrence of an AE will be based on changes in the subject’s signs and symptoms. AEs will be monitored until a subject completes the study unless the Investigator determines the event is related to the investigational device, in which case they will be monitored until resolution if possible. Medical care will be provided, as defined in the informed consent, for any AE related to study participation. AEs will be collected on an AE CRF and applicable source documentation.

The following should not be considered an AE:

- A condition requiring a preplanned procedure unless the condition worsened since screening
- A preexisting condition found as a result of screening, unless the condition has worsened since enrollment.

Document Title: Randomized Controlled Study Comparing Colon Evaluation With The Pure-Vu System To A Standard Colonoscopy In Patients Who Are High Risk For Inadequate Bowel Preparation (“RESCue”)	Document No. CL00048	Version 1.0	Page 31 of 41
---	--------------------------------	-----------------------	---------------

All AEs observed during this study, regardless of severity or relationship to the investigational device will be recorded on the appropriate CRF.

14.9 Reporting Responsibilities

An investigator shall submit to the sponsor and to the reviewing IRB a report of any SAEs, ADEs, SADEs, USADEs, and device deficiencies that could have led to a serious adverse device effect occurring during an investigation within 24 hours of learning of the event, but in no event later than 10 working days after the investigator first learns of the effect.

A sponsor who conducts an evaluation of an unanticipated adverse device effect under 21 CFR Part 812.46(b) shall report the results of such evaluation to FDA and to all reviewing IRB's and participating investigators within 10 working days after the sponsor first receives notice of the effect. Thereafter the sponsor shall submit such additional reports concerning the effect as FDA requests (21 CFR Part 812.150).

15.0 Ethics and Compliance

15.1 Statement of Compliance

This clinical investigation will be conducted in accordance with the ethical principles that have their origin in the Declaration of Helsinki, ISO 14155:2011 (Clinical Investigation of Medical Devices for Human Subjects – Good Clinical Practice), ICH-GCP, and any regional or national regulations, as appropriate.

This may include an inspection by Motus GI representatives and/or Regulatory Authority representatives at any time. The investigator must agree to the inspection of study-related records by the Regulatory Authority/ Motus GI representatives and must allow direct access to source documents to the Regulatory Authority/ Motus GI representatives. Regulatory Authority approvals/authorizations/notifications, where required, will also be in place and fully documented prior to study start.

15.2 Protocol Compliance

No changes to the study protocol will be permitted without the written approval from Motus GI and the IRB. The investigator must notify Motus GI and the reviewing IRB of any deviation from the study

Document Title: Randomized Controlled Study Comparing Colon Evaluation With The Pure-Vu System To A Standard Colonoscopy In Patients Who Are High Risk For Inadequate Bowel Preparation (“RESCue”)	Document No. CL00048	Version 1.0	Page 32 of 41
---	--------------------------------	-----------------------	---------------

protocol when specific to the protection of the life or physical well-being of a subject in an emergency. Such notice must be given as soon as possible, but in no event later than 5 working days after the emergency has occurred. Except in such an emergency, prior written approval by Motus GI is required for changes in or deviations from the protocol. If these changes or deviations affect the scientific soundness of the Plan or the rights, safety, or welfare of human subjects the IRB will also be notified. All other deviations will be reported per the site’s IRB deviation policy. Should any deviations from the study protocol occur, these will be reviewed by Motus GI for their clinical significance. If the event is performed without written approval from all parties, the investigator may be terminated from the study.

15.3 Institutional Review Board (IRB)

Documented approval from the appropriate Institutional Review Board (IRB) will be obtained for all participating centers prior to study start, according to ICH GCP, local laws, regulations, and organization. When necessary, an extension, amendment, or renewal of the IRB approval must be obtained. The IRB must supply to the sponsor a list of the IRB membership and a statement to confirm that the IRB is organized and operates according to GCP and applicable laws and regulations.

15.4 Subject Informed Consent

Prior to the beginning of the trial, the investigator must have the IRB written approval of the ICF and any other written information to be provided to subjects. The written approval of the IRB together with the approved ICFs must be filed in the study files.

The process of obtaining informed consent must be in accordance with applicable regulatory requirement(s) and must adhere to GCP and to the ethical principles originating in the Declaration of Helsinki. Written informed consent must be obtained before any study specific procedure takes place. Participation in the trial and date of informed consent given by the subject should be documented appropriately in the subject files.

15.5 Insurance

All subjects participating in the trial will have insurance coverage by the Sponsor, in accordance to applicable local laws.

Document Title: Randomized Controlled Study Comparing Colon Evaluation With The Pure-Vu System To A Standard Colonoscopy In Patients Who Are High Risk For Inadequate Bowel Preparation ("RESCue")	Document No. CL00048	Version 1.0	Page 33 of 41
---	--------------------------------	-----------------------	---------------

15.6 Confidentiality

All records identifying the subject will be kept confidential and, to the extent permitted by the applicable laws and/or regulations, will not be made publicly available.

Subject names will be kept confidential. Only the subject number and initials will be recorded in the CRF, and if the subject name appears on any other document, it must be obliterated. In cases where the local law does not allow using the subject initials serial number will be appointed (e.g. AAA, BBB). Study findings stored on a computer will be stored in accordance with local data protection laws. The subjects will be informed in writing that representatives of the sponsor, IRB/EC or Regulatory Authorities may inspect their medical records to verify the information collected, and that all personal information made available for inspection will be handled in strictest confidence and in accordance with local data protection laws.

Subjects will also be informed that information regarding the study that does not include subject identifiers will be posted on clinicaltrials.gov.

If the results of the trial are published, the subject's identity will remain confidential.

The investigator will maintain a list to enable subjects' records to be identified.

15.7 Use of Data and Publications

Information regarding the study and study data will be made available via publication on clintrials.gov.

All data and results and all intellectual property rights in the data and results derived from the study will be the property of Motus GI, who may utilize the data in various ways, such as for submission to government regulatory authorities or disclosure to other investigators, educational, further product development and marketing uses.

The investigators, while free to utilize data derived from the study for scientific purposes, must discuss any publication with the sponsor prior to release and obtain written consent of the sponsor on the intended publication. The sponsor recognizes the right of the investigator to publish the results upon completion of the study. However, the investigator must send a draft manuscript of the publication or abstract to the sponsor 45 days in advance of submission in order to obtain approval prior to submission of the final version for publication. This will be reviewed promptly, and approval will not be withheld unreasonably.

Document Title: Randomized Controlled Study Comparing Colon Evaluation With The Pure-Vu System To A Standard Colonoscopy In Patients Who Are High Risk For Inadequate Bowel Preparation (“RESCue”)	Document No. CL00048	Version 1.0	Page 34 of 41
--	--------------------------------	-----------------------	---------------

In case of a difference of opinion between the sponsor and the investigator(s), the contents of the publication will be discussed in order to find a solution which satisfies both parties. This time line can be shortened at the mutual agreement of sponsor and investigators.

Disclosure of involvement in a publication (e.g., sponsor of the study; collection, analysis, and interpretation of data; professional writing assistance) must be as specified by journal-specific policies, submission requirements, and prevailing editorial standards, in addition to those specified by International Committee of Medical Journal Editors. Authors must ensure that an acknowledgement/disclosure statement is included in the body of the manuscript for Motus GI to review for accuracy. All authors must also disclose financial or personal affiliations that could be considered conflicts of interest as per journal requirements.

